## **5.2. Study Product: ME-401**

### **5.2.1. Preparation and Administration of ME-401**

Zandelisib (code ME-401) is provided as 60 mg capsules, which require no preparation prior to administration. Subjects should be instructed to swallow the capsules whole and to not chew or crush them.

ME-401 is dosed on a milligram (mg) basis with no adjustment in dosing based on subject weight. ME-401 is to be taken orally once a day at approximately the same time each day in accordance with the IS dosing regimen (or CS dosing regimen if switched from IS after PD).

ME-401 should be taken with a glass of water on an empty stomach (i.e., at least 1 hour prior to food intake or 2 hours after food intake). If a subject routinely experiences discomfort with dosing, he or she is permitted to take ME-401 with a light, non-fatty snack. If a dose is missed it may be taken up to 12 hours after the specified time. After 12 hours the missed dose should be omitted. If possible, the subject should be advised to separate administration of ME-401 capsules from that of concomitant medications that have a known effect on P-glycoprotein (P-gp) and breast cancer resistance protein transporter (BCRP) (see [Section 5.5](#) for prohibited concomitant medications).

### **5.2.2. Storage of ME-401**

ME-401 should be protected from direct sunlight and stored in a cool place (at the subject's home) or at room temperature, 15–25°C (59–77°F).

### 5.2.3. ME-401 Accountability and Compliance

The Principal Investigator or their representative will account for all ME-401 provided by the Sponsor. All ME-401 will be stored at the site in a secure and locked location. The Principal Investigator shall maintain adequate records of the disposition of ME-401, including dates, quantity, and use by subjects. Upon completion of the study, all remaining ME-401 will be accounted for and unused material will either be returned to the Sponsor (or designee) by a traceable method (UPS, FedEx, etc.) or destroyed (with documentation of drug destruction provided to the Sponsor), as instructed by the Sponsor.

## 5.3. ANTICIPATED TOXICITIES

As of the 09 June 2019 data cut-off date, the most common Grade  $\geq 3$  AEs noted in the Phase 1b study for the 52 subjects administered ME-401 alone consisted of diarrhea/colitis in 14 (26.9%) subjects; neutrophil count decreased in 4 (7.7%) subjects; and ALT increased, AST increased, and rash in 2 (3.8%) subjects each. There were no DLTs reported across all dose levels in the 56-day DLT window period.

Refer to [Section 5.3.1](#) for study drug dose interruption or treatment discontinuation in a subject if such toxicity occurs and is not considered related to the underlying disease. Subject management will be determined by the treating physician and may include administration of a hematopoietic growth factor for neutropenia, administration of corticosteroids for the treatment of colitis, pneumonitis, and other AEs considered immune mediated ([Table 4](#)), and antimicrobial or anti-viral treatment for the prevention and/or management of OIs ([Section 5.4](#)).

Refer to the current Investigator's Brochure for more details.

### 5.3.1. Modified Dosing Schedules

Modification of the dosing schedule and dosing interruptions are utilized for toxicity management in this study. For subjects who experience toxicity during the first 2 cycles while receiving daily therapy with ME-401, dose interruption followed by a switch to intermittent schedule daily dosing for the first 7 days of every 28-day cycle is allowed. Subjects who experience toxicities on the IS will be managed by the instructions for management of potential drug-related toxicity in [Table 4](#), which may include dose interruption or permanent discontinuation of ME-401. All treatment interruptions (including any missed doses, treatment delays) and discontinuations and their reasons are to be recorded in the electronic case report form (eCRF). Interrupted treatment is resumed on the IS after subjects recover to the grade specified in the table (subjects who permanently discontinue ME-401 dosing will proceed to the EOT/30-Day Safety Follow-up visit). Subjects on the IS who recover within the same treatment cycle, will complete the planned days off, and resume treatment on Day 1 of the next planned cycle.

Subjects who interrupt study drug dosing for  $>6$  continuous weeks will have ME-401 permanently discontinued unless restarting ME-401 is authorized by the study Medical Monitor. Consultation with the Sponsor's Medical Monitor or designee is recommended before treatment interruption or discontinuation due to any reason.

**Table 4: ME-401 Toxicity Management**

Toxicity	Grade*	Management of ME-401	Management of Toxicity
Diarrhea/colitis	2	
 
Hold ME-401 unless diarrhea is confirmed to be due to an infectious agent.
 
If ME-401 is held, once diarrhea resolves to Grade <math>\leq 1</math>, resume ME-401 at 60 mg administered on IS (the first 7 days of each 28-day cycle).
 
	
 
If infectious cause of the diarrhea, including clostridium difficile, was ruled out then proceed with following management steps:
 
Hold ME-401 and start loperamide or similar anti-diarrheal agent.
 
If no improvement occurs within 48 hours, start prednisolone 0.5–1 mg/kg IV or oral budesonide 9 mg daily.
 
Based on data from the Phase 1b study, subjects with diarrhea that was preceded by rash in the prior 1–2 weeks often experienced more prolonged and severe diarrhea. Thus, if diarrhea is preceded by rash in the prior weeks, start prednisolone 0.5–1 mg/kg IV or oral budesonide 9 mg daily at the time when a subject experiences rash.
 

	3	
 
Hold ME-401 until AE resolves to Grade <math>\leq 1</math>, then, if clinically indicated, resume ME-401 at 60 mg administered on IS.
 
For recurrence of Grade 3 diarrhea/colitis, discontinue study drug permanently.
 
	
 
Subjects should be hydrated as clinically indicated and administered (methyl) prednisolone 1–2 mg/kg/day IV or equivalent oral systemic steroids. 
 
If no improvement occurs within 2–3 days, the corticosteroid dose should be increased to 2 mg/kg/day IV or equivalent oral systemic steroids.
 
 
 
Once improved to Grade <math>\leq 1</math>, start tapering the corticosteroid as clinically indicated.
 

	4	
 
Permanently discontinue ME-401.
 
	
 
Treat per institutional standard of care.
 

**Table 4: ME-401 Toxicity Management (Continued)**

Toxicity	Grade*	Management of ME-401	Management of Toxicity
Cutaneous Reactions and Mucositis	2	
 
Hold ME-401 unless rash ascertained to be unrelated to study drug.
 
If ME-401 is held, once AE resolves to Grade <math>\leq 1</math>, resume ME-401 at 60 mg administered on the IS.
 
	
 
Monitor subjects and determine cause of rash.
 
Per Investigator's discretion, antihistamines, topical steroids, and systemic steroids may be given.
 

	<math>\geq 3</math>	
 
Hold ME-401 until AE resolves to Grade <math>\leq 1</math>, then, if clinically indicated, resume ME-401 at 60 mg administered on the IS.
 
For recurrence of Grade 3, permanently discontinue ME-401.
 
	
 
Monitor subjects as clinically indicated until resolution.
 
Oral antihistamines and systemic corticosteroids such as prednisone 0.5–1 mg/kg/day (or equivalent dose of methylprednisolone) should be given until rash resolves to Grade <math>\leq 1</math>.
 

	Any	
 
Permanently discontinue ME-401 for life-threatening toxicity, Stevens-Johnson syndrome of any grade, and TENS of any grade.
 
	
 
Treat per institutional standard of care.
 

Hepatotoxicity	2	
 
For ALT/AST <math>>3-5 \times</math> ULN but <math><5 \times</math> ULN, maintain ME-401 treatment dose and schedule.
 
	
 
Monitor ALT/AST weekly until resolved to Grade <math>\leq 1</math> or baseline level.
 

	3	
 
For ALT/AST <math>>5-20 \times</math> ULN, hold ME-401.
 
Resume ME-401 at 60 mg administered on the IS.
 
For recurrence of Grade 3, permanently discontinue ME-401.
 
	
 
Monitor ALT/AST once a week until resolved to Grade <math>\leq 1</math> or baseline level.
 
Treat per institutional standard of care, which may include a course of corticosteroids if clinically indicated.
 
Assess if Hy's law applies.
 

	4	
 
For ALT/AST <math>>20 \times</math> ULN, permanently discontinue ME-401.
 
	
 
Assess if Hy's law applies.
 
Treat per institutional standard of care, which may include a course of corticosteroids if clinically indicated.
 

Non-infectious pneumonitis (NIP)	2	
 
Hold ME-401 until AE resolves to Grade <math>\leq 1</math>.
 
Resume ME-401 at 60 mg administered on the IS.
 
	
 
Rule out infectious etiology of pneumonitis based on institutional guidance, utilizing following methods: chest X-ray, CT scan, pulsometry, nasal swab, sputum culture and sensitivity, blood culture and sensitivity, urine culture and sensitivity.
 
Treat with corticosteroids and per institutional standard of care.
 

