**Table 4: ME-401 Toxicity Management (Continued)**

Toxicity	Grade*	Management of ME-401	Management of Toxicity
		
 
Grade 4 neutropenia without associated symptoms: ME-401 therapy may continue. If symptoms persist despite adequate supportive care, ME-401 should be held until toxicity resolves to Grade <math>\leq 1</math> or baseline values and then ME-401 may be resumed at 60 mg administered on the IS.
 
	
 
Initiate growth factor support if clinically indicated. If subject is receiving filgrastim support or equivalent, CBC should be repeated after 3 days. Weekly CBCs should continue until resolves to Grade <math>< 3</math>.
 

		
 
Grade 4 thrombocytopenia without associated symptoms, ME-401 therapy may continue if Investigator deems safe.
 
	
 
Check platelets every 3 days until resolves to Grade <math>< 3</math>.
 

Other, not listed above, that are considered related to ME-401	2	
 
Holding ME-401 is not required. Continue ME-401.
 
Dosing may continue at the current dose or at 60 mg administered on the IS.
 
	
 
Treat per institutional standard of care.
 

	3a	
 
Hold ME-401 until AE resolves to Grade <math>\leq 1</math> or baseline.
 
Resume ME-401 at 60 mg administered on the IS.
 
For recurrence of the same Grade 3, permanently discontinue ME-401.
 
	
 
Treat per institutional standard of care.
 

	4	
 
Permanently discontinue ME-401.
 
	
 
Treat per institutional standard of care.
 

Abbreviations: AE = adverse event; ALT = alanine aminotransferase; AST = aspartate aminotransferase; CBC = complete blood count; CMV = cytomegalovirus; CT = computed tomography; CTCAE = Common Terminology Criteria for Adverse Events; IS = intermittent schedule; IV = intravenous; NIP = non-infectious pneumonitis; PCR = polymerase chain reaction; TENS = toxic epidermal necrolysis syndrome; ULN = upper limit of normal.

\* Toxicity graded per CTCAE v5.0.

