**Table 5: NCI CTCAE v5.0 Adverse Event Grading System**

Grade	Comments
1	Mild; asymptomatic or mild symptoms; clinical or diagnostic observations only; intervention not indicated
2	Moderate; minimal, local or noninvasive intervention indicated; limiting age-appropriate instrumental ADL a
3	Severe or medically significant but not immediately life-threatening; hospitalization or prolongation of hospitalization indicated; disabling; limiting self-care ADL b
4	Life-threatening; urgent intervention indicated
5	Death related to AE

Abbreviations: ADL = activities of daily living; AE = adverse event

a. Instrumental ADL refer to preparing meals, shopping for groceries or clothes, using the telephone, managing money, etc.

b. Self-care ADL refer to bathing, dressing and undressing, feeding self, using the toilet, taking medications, and not bedridden.

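### Protocol Table 4 puts a Grade 4 cutaneous or mucositis event under two rows, one permitting resumption and one requiring a permanent stop, and does not say which prevails

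*Protocol*

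**What the plan says.** Protocol Table 4 manages cutaneous reactions and mucositis in three rows, labelled Grade 2, Grade ≥3 and Any. There is no separate Grade 4 row.

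- **Grade ≥3 row.** ME-401 is held until the event falls to Grade 1 or lower, "then, if clinically indicated, resume ME-401 at 60 mg administered on the IS". The row's one permanent stop is "For recurrence of Grade 3, permanently discontinue ME-401".
- **Any row.** "Permanently discontinue ME-401 for life-threatening toxicity, Stevens-Johnson syndrome of any grade, and TENS of any grade".

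The footnote to Table 4 gives the scale: "Toxicity graded per CTCAE v5.0". Protocol Table 5, titled as the grading system of that same CTCAE version, describes Grade 3 as "Severe or medically significant but not immediately life-threatening" and Grade 4 as "Life-threatening; urgent intervention indicated".

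Protocol Section 5.3.1 sends the decision to restart back to the table: "Interrupted treatment is resumed on the IS after subjects recover to the grade specified in the table". It does not say what to do when two rows of one block apply to the same event.

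**The concern.** Read literally, the Grade ≥3 label takes in Grade 4. If Grade 4 means life-threatening, as Table 5 has it, one event satisfies a row that allows treatment to resume and another that ends treatment for good. Two sites could treat the same event differently, and each could point to a row of Table 4 in support.

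What is at stake is mainly subject safety. Section 5.3.2 lists cutaneous reactions and oral mucositis or stomatitis of Grade ≥2 among the AESIs, so the conflict concerns re-exposure after a toxicity that the sponsor is watching for. There is a smaller statistical consequence. Stopping treatment for toxicity is a failure event for time to treatment failure (Protocol Section 7.2.4, SAP Section 3.2.5), so the row that a site follows can decide whether and when a subject has that event.

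**Working it through.** No figure has to be reproduced. The check assigns each type of event to the rows it satisfies, using Table 5 to connect grade with life-threatening.

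| Event | Grade ≥3 row | Any row | Outcome |
|---|---|---|---|
| Grade 2, not SJS/TENS | does not apply (Grade 2 row does) | does not apply | one rule |
| Grade 3, not SJS/TENS | hold, may resume; stop on recurrence | does not apply: Table 5 separates Grade 3 from life-threatening | one rule |
| First Grade 4, not SJS/TENS | hold, may resume | permanent stop | two rules |
| Repeat Grade 4, not SJS/TENS | hold, may resume: the recurrence rule names Grade 3 only | permanent stop | two rules |
| SJS or TENS, Grade ≥3 | hold, may resume | permanent stop, stated for every grade | two rows, but the exception is explicit |

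**Does the ≥ sign carry meaning in this table?** Elsewhere it does. The non-infectious pneumonitis block also has a Grade ≥3 row, and there one instruction, permanent discontinuation, serves both grades. Diarrhea/colitis, hepatotoxicity, lung infection/pneumonia and the Other block give Grades 3 and 4 separate rows; the Grade 4 hepatotoxicity row, for example, is to "permanently discontinue ME-401".

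**Is this the only overlap?** No. Under hematological toxicity, one Grade 4 entry holds the drug for thrombocytopenia or neutropenia, while further Grade 4 entries let dosing continue when there are no associated symptoms. The symptom wording separates these cases in part, but the first entry is not limited to symptomatic events.

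**Is precedence stated elsewhere?** Sections 5.1 and 5.3.1 refer back to Table 4. Section 5.7 lists unacceptable related AEs as a reason to stop, without reference to grade. None of them ranks the rows.

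**Would another control catch a misreading?** Section 5.3.1 recommends, but does not require, consulting the Medical Monitor before an interruption or discontinuation. The review required in the synopsis and the notice in Section 5.1 concern discontinuation. Authorization to restart is needed only after more than 6 continuous weeks off drug. A restart within 6 weeks therefore needs no sponsor review.

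**How often might it arise?** The protocol gives only indirect evidence, from Phase 1b:

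- Table 2: Grade 3 rash in 4 of 39 on CS (10.3%) and 1 of 57 on IS (1.8%).
- Table 3: drug-related Grade 3 rash in 3 on CS and 0 on IS; drug-related Grade 3 mucositis in 1 and 0.
- Footnotes to Tables 2 and 3: no Grade 4 or 5 AEs.
- Sections 1.6.2.1 and 1.6.2.2: a Grade 4 TEAE in 4 of 52 on monotherapy and 1 of 38 on the rituximab combination, so 4 + 1 = 5 of 52 + 38 = 90.
- Section 1.6.2.3: 3 of 47 on CS and 2 of 43 on IS, again 3 + 2 = 5 of 47 + 43 = 90.

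The matching totals suggest the same 90 subjects divided in two ways. The type of these Grade 4 events is not stated. If every one had been cutaneous or mucosal, which nothing in the protocol indicates, the observed share would be 5/90 = 5.6% overall and 2/43 = 4.7% on IS. If none were, it would be zero.

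**The case against.** The strongest reply is that the Any row is an exception by construction. Its label spans all grades, and it names three conditions that take an event out of the grade rows. For SJS and TENS everyone would read it that way, and life-threatening toxicity stands in the same sentence. The recurrence rule, which names Grade 3 only, fits a row really aimed at Grade 3 with a loosely drawn label. This reading is plausible and may be what was intended. But the table does not say it, and on this reading the ≥ sign has almost no content.

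A reader might also infer that the two rows issue opposite orders. The documents do not support that. Resumption in the Grade ≥3 row depends on clinical indication, so the row permits and does not command it; holding the drug and never resuming would breach neither row. The conflict is between may resume and must stop. Nor do the documents support the inference that this block is the only one affected, given the hematology entries.

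A narrower objection concerns Table 5. Section 6.2 applies its categories to AEs that CTCAE does not cover, and the term-specific CTCAE criteria for rash and mucositis are not in the documents. Treating every Grade 4 event as life-threatening therefore rests on the general scale. That scale carries the name of the CTCAE version Table 4 uses, and it is the only definition the protocol supplies, so the step is reasonable but is still an assumption.

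Finally, enrollment is closed (Section 8.3) and such events look uncommon. Both facts limit the reach of the problem. Treatment can still continue until progression or unmanageable toxicity, with a possible switch to CS after progression (Section 5.1), so Table 4 still governs anyone on drug.

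**Conclusion.** The point holds as an unresolved overlap. By the protocol's own grade descriptions, a Grade 4 cutaneous reaction or mucositis falls under a row that permits resumption and a row that requires a permanent stop, and no text ranks them. Grade 3 events other than SJS and TENS are not affected.

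The size is small in numbers. The Phase 1b material gives no identified Grade 4 cutaneous or mucositis event, though it cannot exclude one, because the Grade 4 events counted in Sections 1.6.2.1 to 1.6.2.3 are not described. Objective response rate, sample size, alpha and the analysis populations are untouched; any effect on time to treatment failure would come from isolated subjects. The reason to act is the possible consequence of a single misreading, with no required sponsor review of a restart within 6 weeks.

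The conclusion assumes that Table 5's description of Grade 4 applies to these events and that the ≥ sign means what it says.

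**What to change.** The sponsor should reconcile the Grade ≥3 row, both its label and its recurrence rule, with the Any row. Either each grade should carry exactly one study-drug instruction, or the table should state which row prevails when two apply. The hematology Grade 4 entries should be checked in the same revision. Which clinical rule is right is for the sponsor to decide, and nothing here favors either.

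The cost is a table edit, issued to sites as a protocol clarification or carried in the next amendment. No analysis, sample size or SAP text has to change.

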### 4.1. Inclusion Criteria

1. Signed informed consent.
2. Age  $\geq 18$  years (or age of majority).
3. Histologically confirmed diagnosis as defined in the World Health Organization (WHO) classification ([Swerdlow 2016](#)) of:
  - a. FL limited to Grade 1, 2, or 3a; or
  - b. MZL, including nodal, extranodal, and splenic MZL (histopathological report confirming diagnosis must be available during screening procedures).
4. Subjects with relapsed or refractory FL or MZL who received  $\geq 2$  prior therapy regimens. A previous regimen is defined as one of the following: at least two months of single-agent therapy or at least two consecutive cycles of polychemotherapy, autologous transplant, or radioimmunotherapy. Prior therapy must include an anti-CD20 monoclonal antibody (mAb) and an alkylating agent(s). Relapsed or refractory disease is defined as:
  - a. Relapsed disease: disease progression after a response (CR or PR) lasting  $\geq 6$  months
  - b. Refractory disease: no response to therapy (no CR or PR), or response lasting  $< 6$  months
5. At least one bi-dimensionally measurable nodal lesion  $> 1.5$  cm or extranodal lesions  $> 1$  cm in its longest diameter by computed tomography (CT) scan as defined by the Modified Lugano Classification ([Appendix 5](#)).
  - a. Previously irradiated lesions can be selected as target lesions only in cases of unequivocal evidence of progression.
  - b. For subjects with splenic MZL only: diffuse spleen involvement with splenomegaly, which is defined as the splenic vertical length greater than 13 cm.
6. Eastern Cooperative Oncology Group (ECOG) performance status of 0 to 1 ([Oken 1982](#); [Appendix 6](#)).
7. Adequate hematologic parameters at screening unless abnormal values are due to lymphoma per Investigator assessment:
  - a. Absolute neutrophil count (ANC)  $\geq 1.0 \times 10^9/L$  ( $\geq 1,000/mm^3$ )
  - b. Platelet count  $\geq 75.0 \times 10^9/L$  ( $\geq 75,000/mm^3$ )
8. Adequate renal and hepatic function per local laboratory reference range at screening as follows:

- a. Aspartate aminotransferase (AST)/serum glutamic-oxaloacetic transaminase (SGOT), alanine aminotransferase (ALT)/serum glutamic-pyruvate transaminase (SGPT)  $\leq 3.0 \times$  upper limit of normal (ULN)
  - b. Total bilirubin  $\leq 2.0 \times$  ULN or  $\leq 3 \times$  ULN for subjects with Gilbert's syndrome

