Hy's law is defined as: cases of drug-related hepatocellular injury are defined as elevated ALT or AST  $\geq 3 \times$  ULN, plus elevated total bilirubin  $> 2 \times$  ULN without findings of cholestasis (defined as serum alkaline phosphatase [ALP] activity  $< 2 \times$  ULN), and no other reason can be found to explain.

a For Grade 3 AEs not related to study drug, it is upon the discretion of the Investigator if holding ME-401 is warranted. Treatment interruption must be discussed with the Sponsor's Medical Monitor or designee in such cases.

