## **8.5. Treatment Phase**

The treatment phase begins from the time study drug is first administered (Day 1 of Cycle 1), and continues until the subject discontinues study treatment. Each cycle during the treatment period will consist of 28 days and will be denoted numerically (Cycle 1, Cycle 2, etc.).

After the initial 2 cycles of therapy, study visits will occur on Day 1 of each cycle for Cycles 3 to 7, then every 3 cycles thereafter (i.e., Day 1 of Cycle 10, 13, etc.) as long as the subject continues to receive study drug. The modified dosing schedule for AEs is described in [Table 4](#).

Response assessments, as defined in [Section 7](#), will be performed according to the Schedule of Assessments ([Appendix 1](#)) and detailed in [Appendix 5](#). The disease/response assessment will be performed every 2 months ( $\pm 7$  days) for the first 6 months on study, every 3 months ( $\pm 7$  days) during the following 12 months, and every 6 months ( $\pm 14$  days) thereafter.

For those subjects who switch to CS after disease progression on IS, the date of PD will be designated as a new baseline, and subsequent response assessments will be scheduled per the protocol-specified frequency using the new baseline date and CT scan for reference.

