## 9.7. Laboratory Tests

Laboratory tests listed on the Schedule of Assessments ([Appendix 1](#)) will be analyzed at the investigative site's local laboratory and used in all safety analyses and response assessments (see [Appendix 5](#)); PK samples discussed in [Section 7.4](#) will be shipped to a central laboratory for analysis.

The following tests are to be performed:

- CBC with differential: white blood cell (WBC), ANC, red blood cell (RBC), hemoglobin (HGB), hematocrit (HcT), lymphocytes, eosinophils, monocytes, basophils, platelets, mean corpuscular hemoglobin (MCH)
- Serum chemistry: glucose, blood urea nitrogen (BUN) or urea, creatinine, sodium, potassium, chloride, calcium, alkaline phosphatase (ALP), AST, ALT, total bilirubin, total protein, albumin, LDH, phosphorus
- Coagulation: activated partial thromboplastin time (aPTT), prothrombin time (PT)/international normalized ratio (INR)
- Urinalysis: Dipstick or urine test (pH, specific gravity, glucose, ketones, blood, protein)
- Pharmacokinetic sampling (see [Section 7.4](#))
- Pregnancy test
- HIV testing
- Hepatitis B and Hepatitis C testing
- PCR test for CMV
- OI monitoring:
  - CD4 (for subjects with signs of infection)
  - Blood cultures if febrile neutropenia occurs, or when ANC is NCI CTCAE Grade 4
  - PCR for CMV (every cycle for first 6 months of treatment and every 3 months thereafter). If PCR test is positive for CMV, treatment should be delayed until recovery. Treatment of CMV should be initiated based on local SOC. Retreatment

with ME-401 will be allowed without dose reduction once PCR test for CMV is negative.

Subjects with identified risk factors will have the following tests performed:

- CD4 and CD8 count and ratio, c-reactive protein, blood cultures
- Any additional laboratory and diagnostic methods according to local SOC reported as unscheduled laboratory and diagnostic methods of assessment
- Radiological imaging (i.e., chest X-ray or CT scans)

Note: Treatment of the OI that started while on study should be based on local SOC.

- Bone marrow aspiration/biopsy: performed at screening at the discretion of the Investigator and repeated as indicated for subjects with known or suspected marrow involvement. Bone marrow aspiration/biopsy is to include surgical pathology, immunohistochemistry, and flow cytometry as per SOC. Bone marrow aspiration/biopsy is required to confirm a CR when a nodal CR is documented by a CT scan.

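### Table 4 asks for a Hy's law check only above 5 x ULN, although its own footnote starts the definition at 3 x ULN; the Grade 2 row continues dosing and no SAP output pairs ALT/AST with bilirubin

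*Protocol*

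**What the plan says.** Protocol Table 4 (Section 5.3.1) has three hepatotoxicity rows.

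- **Grade 2** (ALT/AST above 3 and up to 5 x ULN): sites are told to "maintain ME-401 treatment dose and schedule". Follow-up is "Monitor ALT/AST weekly until resolved to Grade" 1 or lower, or to baseline.
- **Grade 3** (above 5 to 20 x ULN): ME-401 is held and later resumed on the intermittent schedule, ALT/AST are repeated weekly, and the row adds "Assess if Hy's law applies".
- **Grade 4** (above 20 x ULN): ME-401 is stopped for good, and the same Hy's law instruction appears.

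The footnote states that "cases of drug-related hepatocellular injury are defined as elevated ALT or AST" at or above 3 x ULN, with total bilirubin above 2 x ULN, ALP below 2 x ULN, and where "no other reason can be found to explain".

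The scheduled chemistry panel in Section 9.7 includes "alkaline phosphatase (ALP), AST, ALT, total bilirubin". On timing, Section 8.5 says that "study visits will occur on Day 1 of each cycle for Cycles 3 to 7, then every 3 cycles thereafter".

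SAP Section 8.4 plans by-visit chemistry summaries, tables of Grade 3 and above toxicity for each parameter, and by-subject listings with normal ranges and derived grades. SAP Section 8.3.3 tabulates adverse events of special interest, which include AST/ALT of Grade 2 or higher. SAP Section 5.1 keeps unscheduled and repeat measurements out of summary tables unless otherwise specified, but includes them in listings.

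**The concern.** The definition and the instruction to apply it start at different thresholds. The Grade 2 band lies entirely inside the transaminase limb of the footnote and entirely outside the prompt. In that band the written instruction is to carry on dosing, and the required repeats omit the two analytes, bilirubin and ALP, needed to decide whether the definition is met. No row says what should happen to dosing if it is met, and the Grade 3 row goes on to resumption without an exception.

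At stake is recognition of serious drug-induced liver injury in a trial where transaminase elevation is a named event of special interest. In the Phase 1b intermittent-schedule group (protocol Table 2), increased AST was reported in 11 of 57 subjects, none at Grade 3, so none of those events was at the grade where Table 4 here first asks the question. The split between Grade 1 and Grade 2 is not given.

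The analysis plan does not make up for this, because it reports each liver parameter separately.

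**Working it through.** No power or sample-size figure is involved. The check sets the thresholds side by side and then counts days between required tests.

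**1. Thresholds (Table 4 and its footnote)**

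| Row | ALT/AST, x ULN | ME-401 | Required repeats | Hy's law prompt |
|---|---|---|---|---|
| Grade 2 | >3 to 5 | continue | ALT/AST weekly | no |
| Grade 3 | >5 to 20 | hold, then resume | ALT/AST weekly | yes |
| Grade 4 | >20 | stop | none stated | yes |
| Footnote definition | >=3, with bilirubin >2 and ALP <2 | not stated | not stated | not applicable |

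The definition starts at 3 x ULN and the first prompt comes above 5 x ULN. The unprompted band therefore runs from 3 to 5 x ULN.

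**2. A worked case.** Take ALT 4 x ULN, bilirubin 2.5 x ULN, ALP below 2 x ULN and no other explanation. Since 4 >= 3 and 2.5 > 2, and the remaining two conditions hold, the definition is met. Since 4 is not above 5, no prompt is triggered. The row that applies to ALT 4 x ULN says to continue.

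**3. Intervals between required bilirubin/ALP tests (nominal study days, protocol Appendix 1).** Weekly repeats falling strictly between two panels = gap / 7 - 1.

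- Cycles 1 and 2, panels on Days 1, 8, 15, 29, 43 and 57: gaps of 7, 7, 14, 14 and 14 days, so 0 or 1 repeat.
- Cycles 3 to 7, for example Cycle 4 to Cycle 5: 113 - 85 = 28 days; 28 / 7 - 1 = 3 repeats.
- Cycle 7 to Cycle 10: 253 - 169 = 84 days; 84 / 7 - 1 = 11 repeats.

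If the ALT rise is found on a scheduled panel, bilirubin and ALP are on that sample and only the prompt is missing. A bilirubin rise that begins later may go unmeasured by required tests for up to 28 or 84 days.

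**4. SAP outputs.** With ALT at 4 x ULN, the subject is not counted in the Grade 3 and above table for ALT. If bilirubin and the other components are also below Grade 3, the subject is missing from all of those tables. Scheduled values enter the by-visit summaries one parameter at a time, and a Grade 2 event reported as an adverse event enters the special-interest counts. The weekly repeats are unscheduled and reach only the listings. No output applies the two criteria jointly.

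**5. Baseline limits (protocol Section 4.1, criterion 8b).** Entry requires bilirubin no higher than 2.0 x ULN, or no higher than 3 x "ULN for subjects with Gilbert's syndrome". Bilirubin above 2 x ULN is thus a rise beyond the entry limit for most subjects, but can be a baseline value in Gilbert's syndrome. A combined output has to separate the two groups.

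**The case against.** The facts in Table 4 and the SAP are not in dispute; the case against is about size and importance.

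- **Intervals.** Chemistry is drawn every 7 or 14 days during the two cycles of daily dosing, and the long gaps fall in the intermittent phase. The 11-repeat figure also needs ALT/AST to stay in the Grade 2 band throughout: recovery ends the weekly tests, and a rise above 5 x ULN brings the hold and the prompt. This stands. The 28-day and 84-day figures are upper bounds from Cycle 3 onward.
- **Other Table 4 rows.** The row for other related toxicities holds drug at Grade 3 and stops it at Grade 4, so a severe related bilirubin rise would interrupt dosing whatever the ALT. This narrows the gap to bilirubin above 2 x ULN but below Grade 3. It does not close it, because at Grade 2 that same row also lets dosing continue.
- **Listings.** All collected values, including unscheduled repeats, will be listed, so a combined case can be found by hand. That is true, but it depends on someone reading for it.
- **General safeguards.** Investigator judgement on stopping (Section 5.7), laboratory adverse event rules (6.1), 24-hour reporting of medically important events (6.5 and 6.6) and the DSMB (6.9) all exist. None requires this check. The Investigator's Brochure and DSMB charter were not available and might contain one.
- **Low observed risk.** For the Phase 1b intermittent group, Table 2 shows no Grade 3 AST increase among 57 subjects and Table 3 one related Grade 3 AST/ALT event. This bears on likely frequency, but counts of Grade 3 events say nothing about the Grade 2 band.

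**Conclusion.** The concern holds. A site that follows the Grade 2 row exactly can keep dosing a subject who meets the Hy's law definition printed under the same table, with no required check. The unprompted band is ALT/AST from 3 to 5 x ULN. Within it, required bilirubin and ALP tests may be missing for up to 28 days in Cycles 3 to 7 and up to 84 days after Cycle 7. The SAP offers no display in which such a case would stand out.

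The conclusion rests on nominal visit days and on these two documents. The worked example also assumes that bilirubin of 2.5 x ULN is below Grade 3; the grade boundaries for bilirubin are not reproduced in the documents. The number of subjects affected cannot be estimated. This is a safety-monitoring and reporting weakness that should be fixed; it does not affect the primary response-rate analysis.

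**What to change.** **Protocol Table 4, Grade 2 row.** Require a Hy's law assessment from ALT or AST at or above 3 x ULN, with total bilirubin and ALP measured on the sample that detects the rise and on every weekly repeat. State that a subject who meets the definition is no longer covered by the instruction to continue, and is reported to the Medical Monitor.

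**SAP Section 8.4.** Add a count and a listing of subjects with post-baseline ALT or AST at or above 3 x ULN and total bilirubin above 2 x ULN. Show ALP, baseline ALT/AST, baseline bilirubin and Gilbert's status. Use all post-baseline samples, as an explicit exception to SAP Section 5.1 so that unscheduled repeats count. Present subjects with Gilbert's syndrome or baseline bilirubin above 2 x ULN separately.

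**Cost.** One clarified row, one table and one listing. All four analytes are already in the chemistry panel, so the added burden is bilirubin and ALP results on repeat samples that are being drawn anyway. Enrollment is closed (Section 8.3), so the protocol change helps only subjects still on treatment; the SAP output would cover everyone treated.
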